# **7.2 SPECIFIC AIMS/SIGNIFICANCE:** Specific Aims

- 1. Examine trends in provider decisions in prescribing analgesics and modifying analgesic treatment plans and provider outcomes for satisfaction, certainty and confidence in dosing of analgesics with and without access to Pain Medication and Mental Health DNA Insight TM genetic testing results.
- 2. Examine trends in patients' satisfaction, certainty and confidence in dosing of analgesics between patient groups whose providers had access to Pain Medication and Mental Health DNA Insight TM genetic testing results and those whose providers did not have access to the genetic information.
- 3. Compare patient-reported pain and mental health outcomes between patient groups whose providers had early access to Pain Medication and Mental Health DNA Insight TM genetic testing results to those who had delayed access in the control period and subsequently following later access to the results.

The general aim of this pilot study is to assess the utility of a test that analyzes the DNA of chronic pain patients to determine their metabolic response to common analgesics, anti-depression and anxiolytic medications, to improve provider and patient confidence and satisfaction with the pain treatment plan. The results of the DNA analysis will help guide providers to change or continue the current analgesic regimen. This concept is known as "personalized" or "precision" medicine - the ability to treat patients based on their genetic profile in order to maximize therapeutic effect and minimize or eliminate unwanted side effects.

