#### 7.3 DESIGN

#### 7.3.1 Design type:

This is a prospective, randomized, controlled, observational pilot study analyzing both providers' and patients' perceptions and responses to the DNA Insight test. For this study there will need to be a total of twelve provider groups to be enrolled and 4-8 of each provider's patients will be enrolled in the study. Enrollment will continue of providers until up to 12 providers and 48 patients have been enrolled in the study. Therefore twelve to sixteen military health system primary care providers will need to be consented due to withdrawal of providers prior to

Page 13 of 34

Protocol Title: Patient and provider confidence and satisfaction with the clinical use of CYP genetic variability analysis to guide analgesic treatment: A randomized, controlled pilot study using the Pain

Medication and Mental Health DNA Insight $^{\text{TM}}$  test.

Initial Date Submitted: 02/10/2015 Revision Date: 31 August 2016

referring patients. A total of 48 patients will be enrolled, 4-8 patients for each of the actively enrolled providers (12- 16 providers and 48 patients total). Each provider's patients will be randomized into delayed treatment (Group A) or immediate treatment (Group B) at a 1:1 ratio. Each participating provider will agree to order and interpret a Pain Medication and Mental Health DNA InsightTM test. Results for patients in Group A will be given to the provider with a 3 month delay. Those in the 3 month delay will serve as a comparison group for the period prior to receiving intervention. Results for patients in Group B will be given to the provider without delay, 2-3 weeks after saliva sample collection. The provider will use the results of the Pain Medication and Mental Health DNA InsightTM test to evaluate whether changes of medications are indicated based on the individual patient's genetic profile. A measure of the provider's certainty, confidence, satisfaction, perception of care and global impression of change will be assessed at baseline, prior to obtaining the test results, and after obtaining the test results, as outlined in the data collection section. Patients' pain related self-reported outcomes, certainty, confidence and satisfaction will be assessed at baseline, prior to obtaining the DNA InsightTM test results, and after receipt and implementation of the test results, as described in the data collection section of the protocol.

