  - ♦ Once consented; subject will be allocated into one of the two study groups based on a table of randomized numbers. Subjects' demographic information such as age, gender,

Protocol Title: Patient and provider confidence and satisfaction with the clinical use of CYP genetic variability analysis to guide analgesic treatment: A randomized, controlled pilot study using the Pain

Medication and Mental Health DNA InsightTM test. Initial Date Submitted: 02/10/2015

Revision Date: 31 August 2016

race, email and phone numbers will be collected. (Appendix C2). This will also list their provider study ID number as well. Prior to the first study-related visit with the provider (Visit 0) the subject will be asked to complete the Defense and Veterans Pain Rating Scale (DVPRS) with Supplemental Items (Appendix D), the Brief Pain Inventory Short Form (BPI-SF) Perception of Relief Item over past week (Appendix E), Patient Reported Outcome Measurement Information System (PROMIS) short forms for pain interference (Appendix F), depression (Appendix G) and anxiety (Appendix H), the Patient Perceptions of Care (Appendix I), and Patient Global Impression of Change (Appendix J). The subject will be provided with a list of common opioids and NSAIDs (Appendix K) and be asked their current medications both prescription and OTC/ alternative treatments. (Appendix L).

- ♦ At Visit 0 a saliva sample will be collected by the study coordinator and labeled with a study ID number assigned specifically to that subject and all the samples for that day will be shipped to Pathway genomics following IATA (international air transport association) shipping regulations. Saliva is collected on all patient volunteers regardless of which group they are in. The DNA/ saliva sample will be destroyed 60 days after collection by the Pathway Genomics lab.
- ♦ After the first study-related visit with the provider (Visit 0) the subject will be asked to complete the patient certainty, confidence and satisfaction surveys (Appendix M). This survey will be provided by email.
- ♦ After Visit 0 with the subject the provider will be asked to complete the Provider Perception of Care (Appendix N), the Provider Global Impression of Change (Appendix O), and Provider Certainty, Confidence and Satisfaction surveys (Appendix P). These surveys can be hand-delivered to provider or provided over email.

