- ♦ A member of the research team will query AHLTA to confirm the subject's current analgesic medication regiment at the time of enrollment. All analgesics will be documented as a total daily dose and all opioids will be converted to daily oral morphine equivalents using the Hopkins Opioid Program (www.hopweb.org). These data will be entered into the CRF [(Case Report Form) (Appendix L). A medication will be classified as an analgesic according to (Appendix Q).
- ♦ If the subject is randomized to Group A, there will be a 3-month wait period before the provider will receive the subject's DNA test result. During this time the patient will be scheduled for monthly visits (Visit 1, 2, and 3) with the provider. Each visit will be at least 1 month in advance or as the clinic allows. During these visits the medications may be changed or adjusted according to routine care. Before each visit the subject will be

Protocol Title: Patient and provider confidence and satisfaction with the clinical use of CYP genetic variability analysis to guide analgesic treatment: A randomized, controlled pilot study using the Pain

 $\label{eq:medication} \mbox{Medication and Mental Health DNA Insight}^{\mbox{\scriptsize TM}} \ \ \mbox{test.}$ 

Initial Date Submitted: 02/10/2015 Revision Date: 31 August 2016

asked to complete surveys of Appendix D, E, F, G, H, I, and J. After each visit the subject will be asked to complete survey of Appendix M. After each visit the provider will be asked to complete surveys of Appendix N, O, and P.

- ♦ A report for the subjects study ID number will be returned to the provider within 1-3 weeks of saliva sample collection for subjects in the Group B, and after the 3-month wait period for Group A. The test report has only the subject's study ID on it, so the study coordinator will match the name of the subject with the subject study ID once it returns, so the provider is aware of the name of the subject. The report will be hand-delivered to the Primary Care Manager (PCM) by the study coordinator for use by the PCM at his/her discretion The provider will keep a copy of the results in a research folder for their use at other study visits. The provider will be informed in the ICF and when results are handed to them that the test results are not to be placed in the patient's medical record or shared with another provider.

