- ♦ The Pain Medication and Mental Health DNA report identifies genetic variations that affect how individuals respond to commonly prescribed opioids, pain medications, antidepressants and anxiolytics. A sample report of the mental health component is shown in (Appendix R). In addition to the medications in the sample report, the Pain Medication and Mental Health DNA Insight will also test for genetic variations affecting response to carisoprodol, celecoxib, codeine, fentanyl, hydrocodone, methadone, methotrexate toxicity, oxycodone and tramadol.
- ♦ The provider will use his/her professional knowledge and judgment to interpret the test results and apply those results to the care of his/her patient. The consent form signed by the primary care managers will emphasize the option to consult with a pain specialist, if deemed necessary by the PCM.
- ♦ The subject will be scheduled for a follow-up appointment upon receipt of the Pain Medication and Mental Health DNA Insight Test. Prior to this visit (Visit 1(Group B) or Visit 3(Group A)) the subject will be asked to complete Appendices D, E, F, G, H, I, and J. At this visit the provider will discuss the test results with the subject and adjust or change the subject's medication as he sees necessary based on the genomic information. It is possible the medications will remain unchanged.
- ♦ After Visit 1 the subject will be asked to complete Appendix M, and the provider will be asked to complete Appendix N, O, and P.
- ♦ After implementation of the test results the subject will be scheduled to see the provider monthly for 6 months (Visit 2, 3, 4, 5, 6) and before each visit the patient subject will be

Protocol Title: Patient and provider confidence and satisfaction with the clinical use of CYP genetic variability analysis to guide analgesic treatment: A randomized, controlled pilot study using the Pain

Medication and Mental Health DNA InsightTM test. Initial Date Submitted: 02/10/2015

Revision Date: 31 August 2016

asked to complete Appendix D, E, F, G, H, I, and J. At each visit, the subjects' medications may be adjusted or changed as deemed necessary by the provider. After the visits the subject will be asked to complete Appendix M, and the provider will be asked to complete Appendix N, O, and P. At the last visit the provider will be ask to complete a question about provider usage (Appendix S).

[figure not shown]

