♦ After the last visit (Visit 6), a member of the research team will query AHLTA to determine the patient's current analgesic medication regiment at the end of the study. The subject will asked at that visit what they are taking as well. All analgesics will be documented as a total daily dose and all opioids will be converted to daily oral morphine equivalents using the Hopkins Opioid Program (www.hopweb.org). These data will be entered onto the CRF.

Protocol Title: Patient and provider confidence and satisfaction with the clinical use of CYP genetic variability analysis to guide analgesic treatment: A randomized, controlled pilot study using the Pain

Medication and Mental Health DNA InsightTM test. Initial Date Submitted: 02/10/2015

Revision Date: 31 August 2016

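### The prescribing part of Aim 1 has no specified with-versus-without-access comparison: both timed regimen captures fall when the two groups have the same access to results

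*Combined protocol and SAP*

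**What the plan says.** Section 7.2 opens Aim 1 with prescribing: "Examine trends in provider decisions in prescribing analgesics and modifying analgesic treatment plans". It sets this, together with provider satisfaction, certainty and confidence, against access or no access to the test results. Section 7.3.1 says where the no-access observations come from: "Those in the 3 month delay will serve as a comparison group for the period prior to receiving intervention".

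Section 7.3.4 times two captures of medication:

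- **Enrolment.** The patient is to "be asked their current medications both prescription and OTC/ alternative treatments", and the record is checked: "A member of the research team will query AHLTA to confirm the subject's current analgesic medication regiment at the time of enrollment". Doses are recorded as daily totals and opioids are converted to oral morphine equivalents.
- **End of study.** "After the last visit (Visit 6), a member of the research team will query AHLTA to determine the patient's current analgesic medication regiment". The patient is asked as well, and the same conversion is applied.

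Between these points treatment can change. In Group A's wait, "During these visits the medications may be changed or adjusted according to routine care". After the results are in use, "At each visit, the subjects' medications may be adjusted or changed as deemed necessary by the provider".

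Section 7.3.6 and its Table 1 place delivery of results at Visit 1 for Group B and Visit 3 for Group A. The section lists only surveys for Visits 1 to 6. It closes by saying that medications will be extracted from records at the end of the study and changes documented and analysed. Section 8.0 describes mixed models for self-report measures and a patient-provider concordance analysis.

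**The concern.** The randomised delay is the only period in which one group's providers hold results and the other's do not. If prescribing is recorded only before and after that period, the design feature that would isolate the effect of access is not used for this outcome.

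A before/after change mixes the test with adjustments that would have been made anyway, which the protocol expressly permits. A comparison at Visit 6 keeps the randomisation but compares longer with shorter access, not access with none. Section 7.1 says that the pilot is to supply preliminary data for a fully powered trial. A prescribing effect estimated in either way would be hard to carry into that trial's planning.

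Leaving the window unstated also allows it to be chosen after the data have been seen.

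**Working it through.** The plan gives no sample-size, power or precision figure for prescribing, so there is nothing to reproduce. Section 8.0's 12 provider groups with 4 patients each give 12 × 4 = 48 patients, or 48 / 2 = 24 per group at the 1:1 ratio.

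**1. Access status at each point** (results at Visit 1 for B and Visit 3 for A, from section 7.3.6 and Table 1):

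| Point | A has results | B has results | Timed regimen capture |
|---|---|---|---|
| Enrolment | no | no | yes |
| After Visit 1 until A's report | no | yes | none stated |
| After A's report to Visit 6 | yes | yes | none stated |
| After Visit 6 | yes | yes | yes |

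Both timed captures fall where the groups have equal access status.

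**2. Length of access.** Just before A's report, B has had 3 − 1 = 2 visit intervals and A none. At Visit 6, B has had 6 − 1 = 5 and A 6 − 3 = 3.

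**3. What Visit 6 can show.** Two illustrations, both assumptions: if access has an immediate and constant effect, the expected Visit 6 difference is 0. If the effect builds evenly over B's 5 intervals, the difference is (5 − 3) / 5 = 0.4 of the full effect.

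**4. Other places that could supply the comparison.** The closing sentence of section 7.3.6 states no dates, window or group contrast. Section 8.0 names no prescribing outcome. The contents of the case report form (Appendix L) and the provider forms (Appendices N, O, P and S) are not shown.

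**5. Precision of a control-period comparison.** The documents give no rates of regimen change. Assume p0 = 10, 20, 30 or 40% under routine care and p1 = p0 + 20 or + 30 points with results. The Wald 95% half-width for the difference is

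1.96 × √[(p0(1 − p0) + p1(1 − p1)) / n].

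- n = 24, narrowest (10% v 30%): 1.96 × √[(0.09 + 0.21) / 24] = 0.219
- n = 24, widest (40% v 60%): 1.96 × √[(0.24 + 0.24) / 24] = 0.277
- n = 20 (assumed, to allow for losses), narrowest (10% v 30%): 1.96 × √(0.30 / 20) = 0.240
- n = 20, widest (40% v 60%): 1.96 × √(0.48 / 20) = 0.304

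Newcombe intervals for the same scenarios have half-lengths of 0.221 to 0.258 (n = 24) and 0.242 to 0.279 (n = 20). Randomisation within provider is not modelled.

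**The case against.** **The data may already be planned.** Section 7.3.6 promises that changes will be documented and analysed, which is broader than an end-of-study snapshot. Providers complete forms after every visit, and those forms are not shown. This stands. A reader might infer that the control-period data are not collected or are lost, but the documents do not support that. The silence of the Visits 1 to 6 lists is weak evidence, because the Visit 0 list in the same section also omits medication data that section 7.3.4 plainly collects. Section 7.3.6 is not a complete list.

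**The prescribing data are not simply uncontrolled.** A reader might infer that only an uncontrolled change remains. That is too strong: the Group B versus Group A comparison at Visit 6 is randomised, though diluted.

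**Prescribing is a minor, exploratory outcome.** Aim 1 speaks of trends, none of the research questions in section 7.1 asks about prescribing, and section 8.0 admits that power may be a problem. This lowers the weight of the point but does not remove it. Aim 1 names prescribing first and asks for the with-and-without-access contrast, and the comparison-group statement in section 7.3.1 is general.

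**The added comparison would be imprecise.** This is correct. With a 20-point difference, even the narrowest Wald half-width above, 21.9 points, leaves zero inside the interval. The half-widths describe the proposed estimate and do not measure harm from the present plan.

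**Conclusion.** The point holds as a gap in specification. The two timed captures of regimen and morphine equivalents fall at equal access status, the promised analysis of changes has no window or contrast, and section 8.0 names no prescribing analysis. Followed as written, the plan yields a before/after change, or a randomised comparison of 5 with 3 visit intervals of access. It does not yield the with-versus-without-access comparison of sections 7.2 and 7.3.1.

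Only the prescribing part of Aim 1 is affected. Satisfaction, certainty and confidence are collected at every visit and do have a control-period comparison.

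The conclusion rests on the visit schedule, not on the assumed change rates. It should be fixed, with medium confidence, because the unseen forms could already hold dated changes. Even then, the analysis would still have to be added to section 8.0.

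**What to change.** 1. In sections 7.3.4 and 7.3.6, state that the planned end-of-study AHLTA extraction also records regimen and daily morphine equivalents as of the last date before Group A's report was delivered to the provider, and at the same time since Visit 0 in Group B. Record every report's delivery date.
2. In section 8.0, add one control-period estimate, Group B versus Group A, with 95% confidence intervals: the difference in the proportion with any regimen change, and morphine equivalents adjusted for the Visit 0 value and provider. Label the before/after change as descriptive and the Visit 6 contrast as randomised earlier-versus-later access.
3. Reconcile the Visit 3 passages so that the cut-off is defined. In section 7.3.4 Group A's wait includes Visit 3 ("During this time the patient will be scheduled for monthly visits (Visit 1, 2, and 3) with the provider"), while a later paragraph of that section and section 7.3.6 have results in hand at Visit 3.
4. If the case report form or a provider form already records dated changes, cite it in section 7.3.6 in place of the extra extraction point. The section 8.0 estimate and the defined cut-off are still needed.

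The cost is an amendment and extra abstraction time per patient, with no added visits. The fix relies on AHLTA holding dated prescriptions, which the documents do not state. Capture would probably be retrospective, since the revision is dated 31 August 2016 and section 5.0 expects completion in October 2016. Over-the-counter and alternative treatments between visits would not be captured. The intervals would be wide, about ±22 to ±30 points under the assumed rates, so the result would be for estimation and not for a test.

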# Provider Diagram

[figure not shown]

Protocol Title: Patient and provider confidence and satisfaction with the clinical use of CYP genetic variability analysis to guide analgesic treatment: A randomized, controlled pilot study using the Pain

Medication and Mental Health  $\overline{DNA}$  InsightTM test.

Initial Date Submitted: 02/10/2015 Revision Date: 31 August 2016

#### **Patient Diagram**

Protocol Title: Patient and provider confidence and satisfaction with the clinical use of CYP genetic variability analysis to guide analgesic treatment: A randomized, controlled pilot study using the Pain

Medication and Mental Health DNA Insight  $^{\text{TM}}$  test.

Initial Date Submitted: 02/10/2015 Revision Date: 31 August 2016

#### 7.3.5 Data Collection Instruments:

Appendix 1: Provider Ad

Appendix 2: Patient Ad

Appendix 3: Coordinator Script

Appendix A: Provider Script

Appendix B: Coordinator Contact Information

Appendix C1: Provider Contact information

Appendix C2: Subject demographics and contact information

Appendix D: DVPRS side A and B

Appendix E: BPI-SF Perception of Relief Item

Appendix F: PROMIS SF v1.0 – Pain Interference-SF8a

Appendix G: PROMIS SF v1.0 – ED-Depression-SF8a

Appendix H: PROMIS SF v1.0 – ED-Anxiety-SF8a

Appendix I: Patient Perceptions of Care

Appendix J: Patient Global Impression of Change

Appendix K: Patient Medication Example List

Appendix L: Case Report Form

Appendix M: Patient Certainty, Confidence and Satisfaction

Appendix N: Provider Perception of Pain Care

Appendix O: Provider Global Impression of Change

Appendix P: Provider Certainty, Confidence and Satisfaction

Appendix Q: Medication list of acceptable analgesics

Appendix R: Sample genomics report for both

Appendix S: Provider Usage

References: See Section 6.1

# 7.3.6 Variables/Data Points:

Baseline (Visit 0):

All subjects, regardless of group assignment

Before visit with the provider

- Demographics (Appendix C), DVPRS (Appendix D), BPI perception of pain relief item (Appendix E), PROMIS short forms for pain interference (Appendix F), depression (Appendix G), anxiety (Appendix H)
- patient perception of care (Appendix I)
- patient global impression of change (Appendix J)

At the visit saliva sample is taken and sent for analysis

Protocol Title: Patient and provider confidence and satisfaction with the clinical use of CYP genetic variability analysis to guide analgesic treatment: A randomized, controlled pilot study using the Pain Medication and Mental Health DNA InsightTM test.

Initial Date Submitted: 02/10/2015 Revision Date: 31 August 2016

#### After visit with the provider

- certainty, confidence, satisfaction (Appendix M)

